Aim 2: Establish electrophysiological markers of PMS and iASD using VEPs. This aim has also been completed. We established the stability of VEP amplitudes across two time points, in order to validate this tool as a reliable stratification biomarker capturing excitatory activity. We also showed that individual variability detected by electrophysiological measures was associated with clinical symptoms of PMS and iASD measured in Aim 1, including sensory reactivity. Our data suggest a unique VEP profile of excitatory deficits in PMS that overlaps with a subset of children with iASD. Neural responses show strong test-retest reliability, associations with clinical metrics in PMS and iASD, and in Aim 3 we will now test whether they are useful in stratifying patients with iASD with excitatory deficits.

Aim 3. Evaluate the feasibility of electrophysiological markers as a measure of treatment response. Using a double-blind, placebo-controlled crossover design, we will evaluate the use of electrophysiological markers to detect neural response to growth hormone treatment in 30 children (15 PMS; 15 iASD), all of whom show characteristic VEP waveforms reflecting deficits

in glutamatergic activity pre-treatment. Based on our preliminary data, approximately 50% of patients with iASD show reduced $P_{60-N_{75}}$ responses comparable to PMS; this subset will be targeted for the trial. We expect gamma band VEP activity will be sensitive to growth hormone and will track with clinical response on sensory measures. We will also explore the relation between electrophysiological response, growth hormone dose, and IGF-1 level, by examining VEP activity by time point.

We have completed Aims 1 and 2 of this study and this revised protocol will focus on Aim 3. The expected outcome of this Aim 3 is to establish the feasibility of electrophysiological biomarkers for use in clinical trials in PMS and iASD and define a subset of patients with iASD likely to show clinical response to treatment.

[figure not shown]
RESEARCH STRATEGY

Significance: Overall Scientific Premise

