both demonstrate the characteristic waveform, VEP amplitudes are significantly smaller in iASD for both P_{60} - N_{75} ($p=.005$) and N_{75} - P_{100} ($p=.009$; Fig.3). Moreover, results from frequency domain analyses indicate that children with iASD showed significantly weaker activity in the 30-36 Hz range ($p<.01$) and 38-48 Hz range ($p=.034$), corresponding to gamma band activity. **Cognitive ability has no effect on the results.** In PMS, we see distinct VEP waveforms with smaller P_{60} - N_{75} amplitudes reflecting deficits in glutamatergic activity (Fig. 2B & 3). All PMS participants displayed reduced excitatory responses (absence of P_{60} - N_{75}), compared to both TD and iASD (p 's $<.001$). Across groups, reduced P_{60} - N_{75} amplitude corresponded to greater sensory hyporesponsiveness on the SAND ($n=32$, $r=-.529$, $p=.001$) and SSP ($n=32$, $r=.403$, $p=.022$), suggesting VEP response marks variability in clinical symptoms. P_{60} - N_{75} amplitude also correlated with *SHANK3* deletion size ($\rho = .414$; Fig.3 inlay) where there was significantly reduced amplitude in patients with larger deletions as compared to point mutations in

[figure not shown]

Figure 3. PMS shows significantly smaller VEP amplitudes relative to TD and iASD. Inset: P_{60} - N_{75} amplitude is further reduced with increased size of *SHANK3* deletion.

SHANK3 ($p=.03$). Yet, all patients with PMS display the expected GABAergic positive peak at P_{100} , indicating a specific, dissociable, glutamatergic VEP signature. These results are consistent with work in animal (Bozdagi et al., 2010) and human neuronal (Shcheglovitov et al., 2013) model systems demonstrating the deleterious effects of *SHANK3* deficiency on glutamatergic system function. In an effort to examine the use of VEPs as a stratification biomarker to aid personalized medicine approaches among an otherwise heterogeneous group of children with iASD ($n=27$), our results suggest that approximately 30% display P_{60} - N_{75} amplitudes within one standard deviation of the PMS mean (Fig.4; purple iASD circles below red dotted line), reflecting “PMS-like” excitatory

deficits.

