of iASD with constrained heterogeneity based on a biological marker. Fourth, given our strong preliminary data in PMS and iASD and existing infrastructure and pipeline for conducting clinical trials, we will test the feasibility and robustness of electrophysiological markers in the context of treatment with rhGH, a step which has yet to be taken successfully in the ASD literature. Fifth, we expect to predict a subset of iASD with high potential to respond to treatment with rhGH based on biological profiles related to PMS, making progress toward a more personalized medicine approach for ASD.

Approach

Aim 3: Evaluate the feasibility of electrophysiological markers as a measure of treatment response.

Introduction. The objective of this aim is to administer rhGH to participants with PMS and iASD to evaluate the feasibility of select electrophysiological biomarkers to: 1) detect change in neural response (engagement) and 2) predict treatment responders on clinical assessments (efficacy). We will also explore the relationship between rhGH dose, IGF-1 level, and electrophysiological response. Participants will be selected based on electrophysiological profiles with reduced $P_{60}-N_{75}$ VEP amplitudes, reflecting impaired glutamatergic function. **Approach:** We will employ a randomized, placebo-controlled, double-blind, crossover design with a four-week wash-out period between phases. **Rationale:** Successful completion of this aim will establish feasibility of select biomarkers for detecting treatment response and advance knowledge about developing targeted treatments for PMS and related subsets of iASD with impaired glutamatergic activity. We expect, based on preliminary data, that the knowledge gained will provide evidence of targeted brain engagement with rhGH, a mechanistic pathway, and evidence of clinical efficacy.

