Research Design. The proposed intervention will recruit 15 children with PMS and 15 children with iASD (2-12 years old). Treatment will follow a randomized, placebo-controlled, crossover format with 12 weeks in each treatment phase (rhGH and placebo). This duration was selected based on evidence with IGF-1 in PMS suggesting our clinical outcomes will be sensitive to change within this time frame (Kolevzon et al., 2014). The primary electrophysiological outcomes will be VEP gamma band activity as our preliminary data with PMS in IGF1 suggests it is sensitive to drug effects (Fig. 5). The primary clinical outcome will be the SAND because: a) our preliminary studies suggest improvement on this measure following IGF-1 (Fig. 6), b) it accurately reflects a sensory phenotype characteristic of PMS and is relevant to a substantial subset of iASD, c) it is associated with electrophysiological measures, and d) it has been validated in ASD and ID.

Inclusion criteria: All participants with PMS will have pathogenic *SHANK3* deletions or sequence variants confirmed in clinical genetics laboratories approved by the Clinical Laboratory Improvement Amendments (CLIA). Genotyping will also be used to confirm the absence of known pathogenic copy number variants in the iASD group. Participants with iASD will meet gold standard diagnostic criteria for ASD, confirmed by the Autism Diagnostic Observation Schedule – 2nd Edition (ADOS-2; Lord et al., 2012) and the Autism Diagnostic Interview-Revised (ADI-R; Lord et al., 1994). All iASD subjects will have a reduced neural response defined by $P_{60}-N_{75}$ amplitudes within one standard deviation of the PMS mean. Subjects will be on stable medication and psychosocial treatment regimens for at least three months prior to enrollment.

Exclusion criteria: 1) closed epiphyses; 2) active or suspected neoplasia; 3) intracranial hypertension; 4) hepatic insufficiency; 5) renal insufficiency; 6) cardiomegaly/valvulopathy; 7) allergy to growth hormone or any component of the formulation; 8) comorbid conditions which prevent participation; 8) visual problems which preclude use of VEP.

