Potential pitfalls and alternative strategies. We expect loss of some electrophysiological data due to the severely affected nature of the population; however, this study is well powered and our proposed sample size can accommodate attrition and still detect meaningful differences across a range of responses. We have been successful in recording VEP in more than 70% of patients with PMS seen in our center. We will implement a sensory desensitization and behavioral training protocol and have extensive experience collecting these data from children with ASD, PMS, and severe ID. Moreover, for the VEP, short-duration stimulus conditions are being utilized. In addition, crossover trial designs carry risks of contamination effects, so we have provided a four-week washout period to minimize this risk. We have not observed significant carryover effects in our preliminary data. We believe this design is important because all patients will be afforded the opportunity to receive active medication. Second, the burden of frequent monitoring visits and subcutaneous injections risks increase the risk of subject withdrawal. Given the rigid control of the study procedures, relatively simple measurement techniques, and based on our experience to date, we do not foresee any major loss of data due to drop-outs or missing values. Still, in case of drop-outs we will use the intent to treat principle so all randomized patients will be included in the data analysis. Third, because of concerns about recruitment feasibility, we have established an excellent working relationship with the national PMS Foundation. Fourth, because we are only enrolling patients with iASD with PMS-like VEP amplitudes, we will not be able to test the *specificity* of target engagement and successful treatment response. Finally, if VEPs cannot be established as a biomarker for stratification or efficacy, we still have a wealth of other electrophysiological and clinical outcomes that will provide critical information.

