particularly uncomfortable for children with developmental disabilities and will be kept to a minimum to reduce risks. The procedures for minimizing risk include assisting parents in keeping their child still, the use of a special lounge chair to help the child relax during the procedure, the use of numbing cream if needed to reduce pain, and the use of professionals in the Mount Sinai Clinical Research Center who are trained and certified in blood drawing procedures in children with developmental disabilities.

The risks in participating in the electrophysiology aims of this study are minimal. The physical contacts with the instruments are limited to the standard EEG electrodes placed on the scalp. Electrodes are disinfected between participants. It is possible that as a result of participating in electrophysiological testing, participants may experience fatigue or anxiety. We will attempt to minimize potential discomfort from testing/evaluation by providing frequent breaks during the visits. If the participant finds any discomfort during the EEG intolerable, he or she will be withdrawn from the study. If the participant feels uncomfortable, the participant or his/her parents can tell the investigators and ask to stop the EEG at any time. We will implement a sensory desensitization and behavioral training protocol in which participants will have the opportunity to practice mock EEG procedures over the course of visits. Participants will also receive a social story describing the components of their visit as needed. Visual schedules and positive reinforcement systems (e.g., token economies) will be used throughout testing.

A Data and Safety Monitoring Board (DSMB) has been convened and has primary responsibility for developing the oversight necessary to promptly identify and act upon any adverse events. The DSMB is made up of three physicians who will meet routinely every six months and immediately should a severe adverse event occur (please see attached DSMB Charter).

Adequacy of Protection Against Risks

Recruitment and Informed Consent:

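### Aim 3 describes all 30 children as selected on a reduced VEP, but the inclusion criteria require a VEP of iASD children only, so a PMS child with no usable recording can be randomised

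*Combined protocol and SAP*

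**What the plan says.** Two statements describe VEP-based selection of the whole sample. The Aim 3 paragraph in the aims section says of the 30 children, "all of whom show characteristic VEP waveforms reflecting deficits" in glutamatergic activity before treatment. The Aim 3 Introduction under Approach says "Participants will be selected based on electrophysiological profiles with reduced" P60-N75 amplitudes and does not limit this to one group.

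The criteria under Research Design are narrower. For iASD: "All iASD subjects will have a reduced neural response defined by" P60-N75 amplitude within one standard deviation of the PMS mean. For PMS, the specific requirement is genetic: pathogenic SHANK3 "deletions or sequence variants confirmed in clinical genetics laboratories approved by" CLIA. The only exclusion that mentions VEP is "visual problems which preclude use of VEP".

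Three other places bear on the point:

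- Scientific Premise for Aim 3, on the preliminary data: "All PMS participants displayed reduced excitatory responses".
- Potential pitfalls and alternative strategies: "We have been successful in recording VEP in more than 70% of patients with PMS seen in our center". That section also expects some loss of electrophysiological data, says the sample size can absorb attrition, and commits to including every randomised patient in the analysis.
- Risks to the Subjects: "If the participant finds any discomfort during the EEG intolerable, he or she will be withdrawn from the study".

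The Power Analysis is for baseline to week-12 change in VEP gamma, by paired t-test. It gives 80% power at d=.77 within each group and d=.53 across groups.

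**The concern.** The eligibility list decides who is randomised, and it does not carry the aim's VEP selection through to PMS. A site following it could randomise a PMS child who cannot tolerate the recording or whose EEG is unusable because of movement. That child would supply nothing on gamma-band MSC, the primary electrophysiological outcome. Without a baseline recording, the child would also drop out of the models that use baseline gamma to predict clinical response. The Data Analysis section gives no rule for a missing baseline VEP.

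An iASD child must produce a recording to qualify, so this kind of loss at entry falls on PMS alone. The two groups are then selected differently on recordability, which complicates any comparison between them. The sample size has no allowance for the loss.

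**Working it through.** **Inputs.** Power Analysis: paired t-test on change in VEP gamma, 80% power, d=.77 within group and d=.53 across groups. Data Analysis: two-sided α=.05. Research Design: 15 PMS and 15 iASD. Potential pitfalls: VEP recorded in more than 70% of PMS patients. The 80% and 90% scenarios below are assumptions, chosen to show a range above that bound.

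**Formula.** Power of a paired t-test with n children = P(T > t_crit), where T is noncentral t with n−1 degrees of freedom and noncentrality d√n, and t_crit is the 97.5th percentile of central t on n−1 degrees of freedom. The opposite tail is negligible.

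**Reproducing the plan's figure.**

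- n=15, d=.77: noncentrality .77×√15 = 2.98, t_crit = 2.145, power 79.2%.
- n=30, d=.53: noncentrality .53×√30 = 2.90, t_crit = 2.045, power 80.1%.

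Both match the stated 80%, with every planned child contributing. There is no margin.

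**Usable PMS children.** 15×.70 = 10.5 (10 or 11); 15×.80 = 12; 15×.90 = 13.5 (13 or 14). Adding 15 iASD children gives 25-26, 27 and 28-29 overall. This assumes no iASD loss and no VEP data at any visit from an unrecordable child.

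| PMS recording success | Usable PMS | Power within PMS, d=.77 | Usable overall | Power overall, d=.53 |
|---|---|---|---|---|
| 100% (as planned) | 15 | 79% | 30 | 80% |
| 90% | 13-14 | 72-76% | 28-29 | 77-79% |
| 80% | 12 | 68% | 27 | 76% |
| 70% | 10-11 | 58-63% | 25-26 | 72-74% |

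At 70% success the effect detectable with 80% power rises from .78 to .94-1.00 within PMS, and from .53 to .57-.58 overall.

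**Chance of no loss.** If children are independent, the chance that all 15 PMS children are recordable is .7^15 = 0.5% at 70% success and .9^15 = 21% at 90%. Some loss is likely even in the favourable case.

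**Does another passage close the gap?** The visual-problems exclusion does not reach behavioural non-tolerance or artefact. The general exclusion for comorbid conditions that prevent participation states no recordability rule. The EEG-intolerance rule removes a child from the study but is not tied to a time before randomisation; applied afterwards, it produces missing primary-outcome data in a trial that promises to analyse all randomised patients. The preliminary finding of a deficit in every PMS participant describes children who were recorded, so it says nothing about whether a recording can be obtained.

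**The case against.** The strongest reply is that the eligibility list is incomplete, and that nobody chose to admit PMS children without a VEP. The Aim 3 Introduction states selection on VEP for participants generally, and the preliminary data explain why no PMS amplitude cut-off was written. That is fair as to intent, but the operative criteria still do not contain the rule.

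The protocol also takes steps to limit loss: desensitisation, mock EEG practice and short stimuli. The 70% figure is a lower bound among patients seen at the centre, not among prepared trial candidates. This stands, and it is why the results are shown as a range.

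Three stronger readings are tempting and should be resisted:

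- A reader might take 58-63% as the power of the trial. It is the within-PMS figure at the lower bound. The Power Analysis says its main interest is the overall treatment effect, for which the figure at that bound is 72-74%.
- A reader might infer that a child without a baseline VEP is lost altogether. VEPs are also planned at weeks 4, 8 and 12 of each phase, the model has subject random intercepts, and such a child still contributes to the SAND hyporeactivity subscale (the primary clinical outcome) and to safety.
- A reader might infer that PMS children without the deficit will enter. The preliminary data give no support for that; the gap is in recordability, not amplitude.

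One objection bears on the remedy. Aim 3 is about feasibility, and screening out unrecordable children would flatter the feasibility result unless the screen failures are counted. That stands and is built into the fix.

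**Conclusion.** The point holds as a mismatch between the aim and the eligibility criteria, with a moderate effect on power. The stated power for the overall effect needs all 30 children to supply VEP data. With PMS recording success between 70% and 90%, it falls from 80% to between 72% and 79%; within PMS it falls from 79% to between 58% and 76%. These figures rest on no iASD loss, no later loss in either group, and no VEP data at all from unrecordable children. The first two assumptions are favourable to the plan. The third is unfavourable, because some children may be recorded at a later visit. The statement that the sample size can absorb attrition has no allowance behind it. The documents do not show that the loss will reach 30%, and they do not say whether the baseline VEP comes before or after randomisation. The change should be made; it is not a reason to regard the design as unsound.

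**What to change.** Add to the PMS inclusion criteria a usable VEP recording obtained before randomisation, as iASD entry already requires in effect. Define usable in advance. No separate amplitude cut-off is needed for PMS: every recorded PMS child in the preliminary data showed the deficit, and applying the iASD rule to PMS would define the group by its own mean. Report the number of PMS children who fail this screen alongside the feasibility result.

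**Cost.** One criterion and some extra screening. At 70% success, 15/.70 = 21.4, so about 22 PMS children would be screened to randomise 15; at 90%, 15/.90 = 16.7, so about 17. The Timeline's accrual of one child per group per month should be checked against this in a rare disorder. Results would apply to children who can complete a VEP, which narrows the population in a study meant to include severely affected children.

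**Alternative.** If PMS entry is to stay open regardless of recordability, reword the Aim 3 paragraph and the Aim 3 Introduction so that they no longer describe all participants as selected on VEP. Restate the Power Analysis and the attrition claim under Potential pitfalls for a stated expected VEP loss, and say how a missing baseline VEP will be handled.

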Outcome measures: The primary electrophysiological outcome will be VEP gamma band activity as measured by MSC, which includes frequencies between 30-36 Hz. The secondary electrophysiological outcome will be VEP P₆₀-N₇₅ amplitude. VEP stimuli, data preprocessing, and variable extraction. The primary stimulus condition will be a contrast-reversing checkerboard (100% contrast) of one-minute duration to elicit a transient VEP. VEPs will be analyzed in both time and frequency domains. Waveforms will be standardized into z-scores, segmented to evoking stimuli, filtered 1-100Hz with a 60Hz notch, and averaged across epochs. For time-domain analyses, VEP amplitudes over occipital cortex (Oz) will be measured peak-to-trough (P₆₀-N₇₅, N₇₅-P₁₀₀) and latency (P₆₀, N₇₅, P₁₀₀) will be measured by time-to-peak. Frequency-domain analyses will be conducted using MSC statistics (Zemon et al., 2009, Siper et al. 2016) to quantitatively assess the integrity of overall responses in different frequency bands. MSC reflects response reliability by providing an estimate of signal power relative to the combined power of signal+noise. As such, MSC measures consistency from one trial to the next at a given frequency. A pure signal produces a value of 1 and no signal produces a value of approximately 0.1 (bias level for pure noise); thus, higher MSC values reflect stronger and more consistent oscillatory activity in a given frequency band. Six distinct frequency mechanisms for the tVEP waveform include: Band 1, 6-10 Hz, Band 2, 12-28 Hz, Band 3, 30-36 Hz, Band 4, 38-48 Hz, Band 5, 50-64 Hz (60 Hz electrical noise omitted), Band 6, 66-84 Hz (Siper et al., 2016; Zemon et al, 2009, Zemon & Gordon, in prep.). These MSC frequency bands meet criteria for reliable components regardless of sample size as demonstrated by Monte Carlo computer simulations (Guadagnoli & Velicer, 1988; Stevens, 1996). Based on preliminary data, we expect both P₆₀-N₇₅ amplitude and MSC values in bands encompassing gamma wave activity (Bands 3 and 4) to be decreased in PMS relative to iASD.

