Data Analysis. Following the procedures of a 2x2 cross-over design, each subject is randomized to one of two treatment sequences. First we will use graphical and numerical statistics to characterize treatment-, period- and cross-over effects (Jones & Kenward, 1989). Under the assumption of no cross-over effects and data following an approximate normal distribution, we will fit generalized linear mixed models (GLMMs) to the data examining the effects of group (PMS, iASD), condition (placebo, drug), time (baseline, week-12). Interactions on clinical and VEP measures will be checked for differential treatment effects, including subject level random

intercepts, to control for within subject correlations. Next, we will add baseline VEP gamma band activity, along with its interactions, to the models for clinical outcomes. In particular, a VEP by group by time interaction would suggest that the electrophysiological marker is predictive of differential treatment response. We will repeat these analyses with secondary electrophysiological markers and any derived composites. To examine whether electrophysiological markers track changes in clinical profiles, we will fit an additional GLMM with VEP values included as a time-varying rather than baseline covariate. If treatment effects become less significant it will suggest that rhGH is acting on clinical outcomes through the biomarker. Finally, we will directly correlate week-12 change scores for EEG and clinical measures. In case of major cross-over effects, we will base our primary analysis on phase 1 data only as a parallel group study. All tests will use a two-sided α of .05.

Power Analysis: Power is calculated for drug group differences in baseline to week 12 change scores in VEP gamma power since we are primarily interested in an overall treatment effect rather than a differential effect by group. These correspond to paired t-tests, taking advantage of the crossover design. With α at .05, we have 80% power to detect moderate to large effects ($d=.77$ within each group, $d=.53$ across groups), a reasonable expectation based on the potentially disease modifying effects of IGF-1 and our pilot study, which found a large effect ($d=1.05$) of IGF-1 in PMS on a different primary outcome (ABC-SW).

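### The planned random-intercept model has no period term and is not the paired t-test behind the 80% power; its standard error can err in either direction.

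*Combined protocol and SAP*

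**What the plan says.** Under Approach, Aim 3, Data Analysis, the plan opens with description: "First we will use graphical and numerical statistics to characterize treatment-, period- and cross-over effects". It then states the model: "we will fit generalized linear mixed models (GLMMs) to the data examining the effects of group (PMS, iASD), condition (placebo, drug), time (baseline, week-12"), with interactions to be checked and subject-level random "intercepts, to control for within subject correlations". Neither period nor sequence is listed as a term, no other within-child covariance is given, and no primary contrast is named. The only stated consequence of the descriptive look is a phase-1 analysis if cross-over effects are major.

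The Power Analysis paragraph uses something else: "Power is calculated for drug group differences in baseline to week 12 change scores in VEP gamma power", and "These correspond to paired t-tests, taking advantage of the crossover design". It quotes 80% power for d=.77 within each group and d=.53 across both.

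The Introduction to Aim 3 describes a "crossover design with a four-week wash-out period between phases" and Research Design a "crossover format with 12 weeks in each treatment phase (rhGH and placebo"). The modelled visits therefore fall at about weeks 0, 12, 16 and 28.

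**The concern.** The powered test and the planned test are different procedures. The paired t-test uses one number per child, the drug-minus-placebo difference in change, and takes its error from the spread of that number. The random-intercept model pools several within-child contrasts into one residual, which is valid only if all pairs of visits correlate equally.

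- **Visits within a phase correlate more than visits across phases.** The pooled residual is too big for the contrast of interest, and power is lost.
- **Correlation decays with time.** The closest two visits, weeks 12 and 16, lie in different phases. The residual can then be too small, and type I error rises.

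Period adds a second problem. A level shift at both phase-2 visits cancels from change scores but inflates the model's residual. A period effect on the change itself enters the error of both the model and an unadjusted paired t-test. The documents suggest a source: Risks to the Subjects has children rehearsing mock EEG at successive visits, and Outcome measures says "MSC measures consistency from one trial to the next at a given frequency". Practice that lowers noise could raise MSC more in phase 1. Neither the direction nor the size of such an effect is documented.

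**Working it through.** **Inputs from the documents.** Two-sided α=.05; 15 PMS and 15 iASD; d=.53 (n=30) and d=.77 (n=15); 12-week phases; four-week wash-out.

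**Assumed.** Visit correlations and period effects; visit variance 1; 15 children per sequence; groups balanced over sequence; complete data; no carryover unless stated. The primary contrast is taken as condition by time, which the power paragraph implies. d is in SDs of the true paired difference.

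**1. The plan's figure.** For a paired t-test the noncentrality is d√n on n−1 df.

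- n=30: .53×√30=2.90 on 29 df, power .801.
- n=15: .77×√15=2.98 on 14 df, power .792.

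The 80% is right for that test.

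**2. Standard error of the planned model.** Order the visits as phase-1 baseline, phase-1 week 12, phase-2 baseline, phase-2 week 12. Up to sign, the paired difference has weights c=(−1, 1, 1, −1) and true variance c′Rc, where R is the visit correlation matrix. The random-intercept model in effect uses 4(1−r̄), with r̄ the mean of the six correlations. Hence

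model SE / true SE = √[4(1−r̄) / c′Rc].

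- *Between/within-phase .70/.85.* r̄=(2×.85+4×.70)/6=.75, so 4(1−r̄)=1.00. c′Rc=4(1−.85)=.60. Ratio √(1.00/.60)=1.29.
- *Serial decay .5 per 12 weeks.* The correlations are .5 (twice, within phase), .397 (twice), .794 (weeks 12 and 16) and .198 (weeks 0 and 28). r̄=.464, so 4(1−r̄)=2.14. c′Rc=4+2(−2×.5−2×.397+.794+.198)=2.40. Ratio √(2.14/2.40)=.95.

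**3. Simulated operating characteristics at n=30, d=.53.** The planned model has 120 observations, less 30 child means and 6 within-child terms, leaving 84 df. The last column adds a shift of 0.3 score SD at both phase-2 visits.

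| Assumed correlations | SE ratio | Power | Type I error | Power with level shift |
|---|---|---|---|---|
| Equal, .70 | 1.00 | .82 | 5.0% | .79 |
| Between/within .60/.70 | 1.11 | .76 | 3.0% | .73 |
| .70/.85 | 1.29 | .63 | 1.3% | .58 |
| .50/.75 | 1.29 | .63 | 1.2% | .60 |
| Decay .9 per 12 weeks | 1.07 | .78 | 3.7% | .69 |
| Decay .8 | 1.03 | .80 | 4.5% | .77 |
| Decay .7 | 1.00 | .82 | 5.2% | .80 |
| Decay .6 | .97 | .84 | 5.8% | .82 |
| Decay .5 | .95 | .85 | 6.3% | .83 |
| Decay .3 | .91 | .86 | 7.6% | .85 |

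**4. Period effect on the change.** Let the phase-2 change be lower by p SDs of the paired difference. With balanced sequences this adds +p to D in one sequence and −p in the other, so the unadjusted test behaves roughly as if d were .53/√(1+p²).

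| p | Paired t, approximate formula | Paired t, simulated | Planned model, simulated |
|---|---|---|---|
| 0.25 | .777 | .78 | .62–.85 |
| 0.5 | .709 | .72–.73 | .58–.82 |
| 1 | .510 | .50–.51 | .44–.67 |

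**5. Period-adjusted within-child difference.** Regressing D on sequence (±1) and centred group leaves 27 df. Power is .79–.80 and type I error 4.6–5.3% in every setting of steps 3 and 4. Analytically, power goes from .801 on 29 df to .800 on 28 df.

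**6. Two smaller edits.**

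- *Adding only a period main effect* leaves power at .64 for .70/.85 and .50/.75.
- *Adding a subject-by-phase random effect with non-negative variance* gives type I error of 5.6–8.4% under decay .9 to .3. The two change scores are negatively correlated there: at decay .5 their covariance is 2(.397)−.794−.198=−.20, with variance 1 each. A variance component cannot go below zero to match that.

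**The case against.** The strongest reply is that the paragraph is under-specified and not wrong. It follows crossover procedures, cites a crossover text, looks at period effects first, and does not say that its listed terms are the only ones. That is fair as a reading. But an analyst who fits what is listed gets the model examined here, and adding period alone does not repair the standard error.

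Several limits stand:

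- The paired t-test has no period term either, so period is not what separates the two tests. Under equal correlation the planned model does slightly better than the stated 80%. With a period effect on change it can also beat the unadjusted paired test (.77 against .73 at p=0.5, equal correlation).
- Type I error exceeds about 5.2% only when the 12-week correlation is .6 or lower. The document reports strong test-retest reliability, including a figure above .93 under Figure 2. That figure concerns amplitude across the epoch and not MSC between visits, so it does not settle the matter, though it does not favour the low-correlation settings.
- The level shift costs little at decay .7 or lower. The .58–.63 figures depend on two assumed correlation pairs.
- At d=.77 with n=30 the planned model still has power .95 in its worst pairs, against .98.
- If drug-first children carry 0.3 SD into the phase-2 baseline that is gone by week 12, the adjusted difference rejects more often under the null: 17.8% against 6.9% at .70/.85, and 12.7% against 4.5% at .50/.75. Both analyses estimate the same biased contrast. In these two settings the planned model rejects less only because its standard error is about 1.29 times too large, which is not protection against carryover.

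**Conclusion.** The concern holds. The 80% figure is correct for a test the plan does not list as its analysis. The listed model's performance depends on a correlation pattern the documents do not report. Over the assumed patterns without a period effect, its power runs from .63 to .86 and its type I error from 1.2% to 7.6%. Unmodelled period effects can lower power further. Direction and size in this trial are unknown, and under equal correlation with no period effect the listed model is sound. This should be changed before unblinding, because the remedy removes the dependence at almost no cost. Confidence is medium, since every magnitude rests on assumed correlations, balanced sequences, complete data and no carryover.

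**What to change.** Name the primary contrast: the within-child drug-minus-placebo difference in baseline to week-12 change. Regress it on sequence coded +1/−1 (this is the period adjustment) with diagnostic group as a centred covariate, and test the intercept. State power for that same test.

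The intent-to-treat statement under Potential pitfalls calls for keeping children with one usable phase. To do so, fit the two change scores per child with condition, period, group and group-by-condition. Use a compound-symmetry covariance that may be negative, not a child random intercept. With complete data this gives the same test. Baseline-adjusted analyses and weeks 4 and 8 can remain optional sensitivity analyses.

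The cost is a short change of plan wording and one or two degrees of freedom (29 to 28, or 27 with group), with no new data.

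The fix does not handle carryover. An assumed 0.3 SD shift that lasts through all of phase 2 cancels, and type I error stays at about 5%. If the shift is present at the phase-2 baseline but gone by week 12, type I error over the correlation settings is 7–23% for the adjusted difference and 4–19% for the planned model. The planned carryover check is still needed.
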